10.3.2 Previous Biomicroscopy

This test will be performed in consecutively from the eyelids and eyes adnexa to the ocular surface and anterior chamber. The following items must be tested:

- ❖ Description of eyelids, eyelashes and adnexa glands.
- ❖ Description of lid wiper, bulbar and fornix: in this item, the qualitative characteristics will be classified as follows.
- ❖ Conjunctival hyperemia:
 - Bulbar hyperemia: it will be compared to the images of Fig. 10.3.3.1, which shows different grades of venous turgor: very slight, slight, moderate and severe.

Fig. 10.3.3.1 ¹⁰

- Tarsal hyperemia: similarly, tarsal hyperemia will be compared with the images shown in Fig. 10.3.3.2, which shows the venous turgor in the palpebral mucosa.
- Documentation in the FRC: the most severe hyperemia must be recorded.

Fig. 10.3.3.2 ¹⁰

10.3.2.1 Anterior Segment:

- ❖ The photometer and consensual pupillary reflexes must be reviewed, as well as the iris constitution, highlighting pathological aspects, such as inflammatory membranes, anterior and posterior synechiae, among others.
- ❖ The width of the anterior chamber will be qualitatively graded using the Van Herick technique, which consists of grading the space between the iris and posterior side of the cornea by subjective appreciation, locating the beam of light of a slit lamp in the external third of the anterior chamber:

Example: Van Herick II

- ❖ Lens: the items to be evaluated are the integrity of the anterior capsule of the lens and its composition characteristics, highlighting only pathological aspects, for example: pseudoexfoliation, pigment, synechiae, etc.

- ❖ Opacities: will be analyzed, if applicable, according to the LOCS II scale.

It will be recorded in FRC as normal/abnormal. If abnormal, it must be specified if this finding affects the protocol procedures and if it prevents the subject from remaining in the study.

[figure not shown]

[figure not shown]
Image 2. LOCS III ⁶

10.3.2.2 Fluorescein Dye

Sodium fluorescein dye dissolved in tetracaine will be used on the ocular surface (billiard conjunctiva and cornea). After staining the surface, the following explorations will be performed:

10.3.2.2.1 Tear Film Breakup Time

It will be measured after blinking once and the patient will be asked to not blink again until the tear film breaks on the cornea. If it is more than 10" it will be regarded as normal. The whole number value will be recorded on the FRC.

Example:

10.3.2.2.2 Epithelial Defects

After the TRL test, the grade of epithelial staining in the cornea and conjunctiva will be tested according to the Oxford University scale, as it has been shown to be the scale closest to the OSDI score.⁷ The record in the FRC must correspond to this scale. It must be recorded in the FRC with the roman numeral corresponding to the grade.

10.3.2.3 Lissamine Green Dye

Lissamine green dye dissolved with tetracaine will be used on the ocular surface (bulbar conjunctive and cornea). Once the surface is stained, the cornea and conjunctive epithelium will be testes according to the Oxford University scale. It must be recorded in the FRC with the roman numeral corresponding to the grade.

Panel	Grade	Criteria
A 	0	Equal or less than panel A
B 	I	Equal or less than panel B, more than A
C 	II	Equal or less than panel C, more than B
D 	III	Equal or less than panel D, more than C

E 	IV	Equal or less than panel E, more than D
> E	V	More than panel E

10.3.3 Measurement of Intraocular Pressure

After testing the ocular surface using fluorescein dye, PIO will be measured using a Goldman tonometer and cobalt-blue filter.

The whole number value will be recorded in the FRC.

10.3.4 Posterior Segment Exploration

The posterior segment will be reviewed to verify that there are no pathological processes requiring attention and/or preventing the participation of the subject in the clinical trial.

The posterior segment and the rest of the retina will be explored under medicinal mydriasis, recording the following aspects:

1. Appearance of vitreous humor
2. Retina completely applied
3. Vascular alterations
4. Appearance of clinical macular area
5. Appearance of the foveolar area
6. Characteristics of the optical nerve
 - a) Emergence of vessels
 - a. Neuroretinal rim
 - b. Cup-to-disc ratio expressed in decimals
7. Report any other clinical finding in the retina.

It must be reported in the FRC as normal/abnormal. If it is abnormal, it should be specified if this finding affects the protocol procedures preventing the subject from remaining in the study. The optical nerve must be reported in decimals.

10.4 Ocular Symptomology

It refers to the enquiry performed by the researcher for the presence or absence of the following symptoms: burning, foreign body sensation and photophobia, related to pterygium. It must be recorded as present or absent. Symptomology directly related to the administration of the drug product must not be reported in this section. Post-instillation symptoms shall be recorded in the instrument "subject's diary".

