9. STUDY SCHEDULE

Procedure	SCHEDULE (window periods)				
	Baseline visit	Visit 1	Visit 2	Final visit	Follow-up call
	Day 1	Day 7 (± 2)	Day 15 (± 2)	Day 21 (± 2)	Day 36 (± 2)
Eligibility criteria (inclusion and exclusion)	X				
Pregnancy test (if applicable)	X			X	
Informed consent signature	X				
General and ophthalmic medical record	X				
Ocular symptomatology (A, B, C)	X	X	X	X	
OSDI questionnaire	X	X	X	X	
Subject code assignment	X				
Visual capacity	X	X	X	X	
Previous biomicroscopy (D)	X	X	X	X	
Testing of epithelial defects with fluorescein dye	X	X	X	X	
Testing of epithelial defects with lissamine green dye	X	X	X	X	
Breakup time	X	X	X	X	
PIO measurement	X			X	
Posterior ophthalmoscopy under mydriasis	X			X	
Treatment delivery	X				
Start of drug application	X				
End of drug application				X ¹	
Drug return				X	
Subject diary submission	X				
Subject diary review		X	X	X	
Evaluation of adverse events		X	X	X	X
Evaluation of concomitant drug	X	X	X	X	
Follow-up call					X

9.1 Annotations to Activities Schedule:

- A. Burning
- B. Foreign body sensation
- C. Photophobia
- D. Includes testing of conjunctival hyperemia variable

¹ The application ends one day before to fulfill the 20 days indicated in the treatment.

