10.6 Subject's Diary Submission and Review

During the baseline visit, the subject will be provided with the instrument "subject's diary" and it will be explained how to fill it out.

During the following visits, the completeness of the diary will be reviewed, and questions that might have arisen during its completion will be answered.

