13.1 Tolerability study

The security variables of the use of Zebesten ® will be evaluated in the appointed visits in the chronogram, by means of the following parameters.

1. burning
2. Foreign body sensation
3. Photophobia

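### Tolerability (13.1) is defined by three symptoms whose visit record (10.4) must leave out symptoms directly related to the drug, so the result as defined reflects pterygium symptoms instead

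*Combined protocol and SAP*

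**What the plan says.** Under the heading "13.1 Tolerability study", the protocol says that the safety variables "will be evaluated in the appointed visits in the chronogram, by means of the following parameters", and lists three: burning, foreign body sensation and photophobia. Nothing else counts towards tolerability.

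The schedule in section 9 collects them in a single row, "Ocular symptomatology (A, B, C)", at baseline, visits 1 and 2 and the final visit. The variables table in 13.3 gives the method for each as direct questioning, recorded as present or absent.

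Section 10.4 governs that questioning. It describes an enquiry about "burning, foreign body sensation and photophobia, related to pterygium". It then rules: "Symptomology directly related to the administration of the drug product must not be reported in this section". The next sentence sends the excluded symptoms elsewhere: "Post-instillation symptoms shall be recorded in the instrument" called the subject's diary. Section 10.6 says of later visits that "the completeness of the diary will be reviewed" and that the subject's questions about filling it in will be answered.

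The Summary (section 6) and section 13 also list the same three symptoms as secondary outcomes.

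**The concern.** A tolerability result should show how well the drops themselves are tolerated. Here the definition in 13.1 points to a record from which recognised drug-caused symptoms are barred. The two rules contradict each other: an investigator who obeys 10.4 cannot supply what 13.1 is meant to report.

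At stake is how the tolerability table will be read. It could show no difference between arms when bromfenac stings more than placebo. If bromfenac relieves pterygium symptoms, the table could even show better tolerability on bromfenac, because relief of the disease and absence of intolerance are recorded as the same answer.

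**Working it through.** The plan states no figure on this point, so there is none to reproduce. The check traces the three symptoms through the protocol.

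1. **Definition (13.1).** Three symptoms, at the scheduled visits. Adverse events and the diary are not mentioned.
2. **Collection (section 9).** One row carries the three symptoms by name. It is marked at baseline too, and section 11.1 places the symptom enquiry before the start of treatment. A baseline value suits a disease-symptom measure; before the first dose there is nothing to tolerate.
3. **Method (13.3).** Direct questioning, present or absent. The diary is not named as a source.
4. **Recording rule (10.4).** Pterygium-related symptoms only; symptoms directly related to administration are barred.
5. **Destination of the barred symptoms (10.4, 10.6).** The diary. Sections 10.7 and 10.8 expressly require adverse events and concomitant drugs to be entered in the case report form. Section 10.6 has no such instruction for diary entries, and section 13 does not list the diary or post-instillation symptoms as a variable.

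Steps 1 to 4 lead to one record. For a given symptom and visit, let D mean a symptom judged related to pterygium and A a symptom judged directly caused by the drops. Section 10.4 records D and omits A. The between-arm result under 13.1 is therefore

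P(D | bromfenac) − P(D | placebo),

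which has no term in A. Two consequences follow:

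- If the arms differ only in A, the expected difference is 0, however large the difference in A.
- If bromfenac lowers D, the difference favours bromfenac, even if A is more frequent on bromfenac.

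Both assume correct attribution. If some drug-caused symptoms are wrongly judged to be pterygium symptoms, they enter the record, which then mixes the two causes in one yes/no item. The documents give no basis for estimating how often that would happen.

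**The case against.** The strongest reply is that drug-caused symptoms have another route into the results. Adverse events are a primary outcome (sections 6 and 13) and a safety parameter (13.2). They are evaluated at visits 1 and 2, the final visit and the follow-up call. The definition in 17.1.1 covers any unfavourable and unintended symptom temporally associated with the product, whether or not related to it, and 17.5.6 asks for an active search. The bar in 10.4 applies only to its own section. This stands. A reader might infer that all drug-caused symptoms would be absent from the analysis, and the documents do not support that. But 13.1 does not include adverse events, 10.4 sends these symptoms to the diary, no rule says when a diary symptom becomes an adverse event, and the sources named in 17.5.6 do not include the diary. Capture by this route is possible but not assured.

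Other points on that side:

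- **No tolerability objective is stated.** Section 5 names efficacy and safety, and its safety objective rests on staining, intraocular pressure and breakup time. One might infer that a trial aim goes unanswered; the text supports only that the result defined in 13.1 does not measure what its heading says.
- **Section 14 does not single out the diary.** It names no outcome variable at all and assigns tests by type of variable. The sound criticism is the diary's absence from section 13.
- **Secondary status does not make the symptoms a benefit measure.** Section 13.3 lists only hyperemia and the OSDI score as efficacy parameters, and the secondary list also holds visual capacity and intraocular pressure, which 13.2 treats as safety. The disease reading comes from 10.4's own limit to pterygium.
- **13.1 does not cite 10.4, and diary review is also in the schedule.** True, but the method given in 13.3 is direct questioning, which makes the 10.4 enquiry the likelier source.
- **The OSDI (Appendix 3) asks about light sensitivity and grittiness whatever the cause.** It is recorded as a single score and classed as efficacy, so it does not supply the tolerability result.

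**Conclusion.** The contradiction holds. As defined, the tolerability result excludes drug-caused symptoms that are recognised as such, and reflects pterygium symptoms. This rests on reading 13.1 together with the schedule row, the direct-questioning entry in 13.3 and the rule in 10.4, and on investigators following 10.4 and attributing symptoms correctly.

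The size cannot be put in numbers of subjects. The documents give no rate of instillation symptoms in either arm, and the placebo contains the same excipients as Zebesten, including benzalkonium chloride (8.2), so even the gap between arms is unknown. It also remains open whether the diary itemises the three symptoms, since the diary form is not among the documents.

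This should be corrected. It affects a defined safety-related result, but not the hyperemia or breakup-time results, and drug-caused symptoms may still appear in part as adverse events.

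**What to change.** - In 13.1, define tolerability as post-instillation burning, foreign body sensation and photophobia from the subject's diary. Confirm that the diary itemises these three symptoms, and revise it if it does not.
- Add matching case report form fields, and state in 10.6 that diary entries are transferred to them.
- List post-instillation symptoms as a variable in section 13.
- In section 14, report for each symptom the proportion of subjects affected per arm, with a 95% CI for the difference, alongside related ocular adverse events. Count each subject once, because 7.2 lets a subject with bilateral pterygium contribute two cases.
- Keep the 10.4 enquiry, unchanged, as the pterygium-symptom secondary outcome only.

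The cost is small: protocol wording, data entry, and possibly a minor revision of the diary or case report form. No new visit or examination is needed.

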10.5 OSDI Questionnaire

It refers to the application of the OSDI questionnaire. The obtained score must be recorded. The score is obtained as follows:

$$OSDI = \frac{(score\ sum)25}{\# \ of \ answered \ questions}$$

10.6 Subject's Diary Submission and Review

During the baseline visit, the subject will be provided with the instrument "subject's diary" and it will be explained how to fill it out.

During the following visits, the completeness of the diary will be reviewed, and questions that might have arisen during its completion will be answered.

10.7 Adverse Events Evaluation

It refers to the evaluation performed by the main researcher for the presence of adverse events according to item 17. Adverse Events.

If the subject presents any adverse event it must be recorded in the file and FRC.

10.8 Evaluation of Concomitant Drugs

The main researcher will question the subject on the use of drug products other than those indicated in the protocol.

If the subject uses any other drug it will be documented in the file and FRC.

11. PROCEDURES TO BE PERFORMED ON EACH VISIT

The procedures to be performed on each visit are listed below. The study day on which the visit must be performed appears in brackets and the permitted window period in parentheses.

11.1 Baseline Visit

1. During this visit it will be evaluated if the subject meets the eligibility criteria.
2. First, the informed consent will be reviewed clarifying any doubt the subject wishes to review, and documenting in the clinical note the subject's possible questions and the answers given to them. This procedure will be performed strictly by the healthcare personnel, preferably by the main researcher.
 - a. Afterwards, the informed consent will be signed, jointly with two witnesses (if applicable).
3. If applicable (female subject in reproductive age), pregnancy test.
4. The medical staff will generate a medical record based on the systems review of the subject, specifying signs and symptoms related to systemic inflammatory diseases. A complete ophthalmic medical record will be generated, including at least the items required in the case report form plus the items required by the usual medical record used for the first time in the subject's research center.
5. OSDI questionnaire will be applied.
6. Ocular symptomology enquiry.
7. Complete ophthalmic exploration, indicating pterygium.
8. Subject code designation (as per item 16. Identification Procedures).
9. Treatment deliverance (as per item 8. Study Drugs).
10. Start of the treatment.
11. Subject diary submission.
12. Concomitant drug products assessment.
13. Scheduling subsequent visits.

11.2 Visits 1 and 2 [Days 7 and 15 (± 2 Days)]

1. Ophthalmic physical exploration:
 - a. Visual capacity testing
 - b. Previous biomicroscopy
2. OSDI questionnaire application
3. Enquiry regarding ocular symptomology
4. Subject diary review
5. Adverse events evaluation
6. Concomitant drug products assessment

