11.3 Final Visit [Day 21 (± 2 Days)]

1. If applicable (female subject in reproductive age), pregnancy test
2. OSDI questionnaire application
3. Ocular symptomology enquiry
4. Complete ophthalmic exploration
5. Return of drug
6. Adverse events evaluation
8. Concomitant drug products assessment

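### Section 11.2 lists the symptom questions after an examination that uses tetracaine, unlike 11.1 and 11.3, which puts the Day 7 and Day 15 symptom data at avoidable risk

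*Combined protocol and SAP*

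**What the plan says.** **Order of items.**
- Baseline (11.1): OSDI is item 5 and the symptom enquiry item 6. The examination follows as "7. Complete ophthalmic exploration, indicating pterygium".
- Visits 1 and 2 (11.2): the list opens with "1. Ophthalmic physical exploration", whose second part is "b. Previous biomicroscopy". OSDI comes next as item 2, then "3. Enquiry regarding ocular symptomology".
- Final visit (11.3): OSDI is item 2, then "3. Ocular symptomology enquiry", then "4. Complete ophthalmic exploration".

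**What the examination contains.** Section 10.3.2.2, numbered under 10.3.2 (Previous Biomicroscopy), states: "Sodium fluorescein dye dissolved in tetracaine will be used on the ocular surface". Section 10.3.2.3 does the same for lissamine green. The section 9 schedule marks both dyes at all four visits.

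**What is asked.** Section 10.4 records burning, foreign body sensation and photophobia as present or absent and gives no recall window. The OSDI form (Appendix 3) asks about the last week. The three symptoms are secondary outcomes (sections 6 and 13) and are the only parameters listed in the tolerability section (13.1). OSDI is secondary and is also an efficacy parameter (13.3).

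**What is analysed.** Section 14 plans intra-group and between-group tests and names no visit for either.

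**The concern.** A patient-reported symptom should be collected under the same conditions at every visit. Here the listed order changes at the two middle visits, and the step that moves ahead of the questions numbs the eye. A present/absent answer with no stated recall window can easily be given about how the eye feels at that moment.

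If that happens, symptoms look better at Days 7 and 15 than they are, in both arms, and return at Day 21 when the questions again come first. The Day 7 and Day 15 changes would then mix treatment with anaesthesia, the rise at Day 21 could be misread as loss of effect, and tolerability at the middle visits would look too good. Data collected in this way cannot be corrected afterwards.

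**Working it through.** The plan states no figure on this point, so there is none to reproduce. The check compares the sections and then illustrates size on stated assumptions.

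**Step 1. Position of the questions and the examination.**

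| Visit | OSDI | Symptoms | Examination |
|---|---|---|---|
| Baseline (11.1) | 5 | 6 | 7 |
| Visits 1 and 2 (11.2) | 2 | 3 | 1 |
| Final (11.3) | 2 | 3 | 4 |

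Only 11.2 lists the examination first.

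**Step 2. Are the dyes part of item 1 in 11.2?** Section 11.2 does not name them. The schedule requires both at these visits, their procedures sit under the biomicroscopy heading in 10.3.2, and no other item in 11.2 could cover them. They therefore belong to item 1.

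**Step 3. Direction of effect.** Let p be the true proportion with a symptom and m the share masked by anaesthesia, equal in both arms. The observed proportion is p(1 − m).
- Within an arm with no true change: observed change = p(1 − m) − p = −pm, a spurious improvement.
- Between arms: observed difference = (1 − m) × true difference. It shrinks, and it stays at 0 if the true difference is 0.
- Baseline to final visit: m = 0 at both ends as listed, so there is no effect.

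**Step 4. Illustration.** The following are assumed and not in the documents: 60% symptomatic at baseline; at Visit 1 or 2, truly 60% on placebo and 40% on active; 69 independent eyes per group (69 is the pre-loss figure in 12.4). The probability of significance at two-sided 0.05 is Φ[(|d| − 1.96 × SE0)/SE1], where SE0 is the pooled and SE1 the unpooled standard error. The within-group column treats the two visits as independent samples.

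Worked example at m = 0.25:
- Between arms: 0.45 against 0.30, d = 0.15. SE0 = √(2 × 0.375 × 0.625/69) = 0.0824. SE1 = √[(0.45 × 0.55 + 0.30 × 0.70)/69] = 0.0814. Φ[(0.15 − 0.1615)/0.0814] = 44%.
- Placebo, baseline against visit: 0.60 against 0.45, SE0 = 0.0850, SE1 = 0.0841. Φ[(0.15 − 0.1666)/0.0841] = 42%.

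| m | Placebo change (truly 0) | Chance it is significant | Between-arm difference | Power |
|---|---|---|---|---|
| 0 | 0 | 5% (nominal) | 20 points | 65% |
| 0.10 | −6 points | 11% | 18 points | 57% |
| 0.25 | −15 points | 42% | 15 points | 44% |
| 0.50 | −30 points | 95% | 10 points | 27% |

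**Step 5. Sensitivity to the test and inputs.** A simulation with 50% prevalence, 80% of symptom states persisting between visits, 69 eyes and no true change gives these chances of a false within-group improvement at 10%, 20% and 30% masking:
- exact McNemar test: about 10%, 30% and 58%;
- ordinary chi-squared on the two visits' frequencies: about 2%, 13% and 39%.

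With the McNemar test at 20% masking, the result runs from 18% at 60% persistence to 40% at 90% persistence. The direction is stable; the size is not.

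**The case against.** The strongest reply is that section 11 says only that the procedures are listed and never makes the order binding. The lists are visibly not chronological: in 11.1, consent is item 2 yet is described as coming first, and concomitant drugs are assessed at item 12, after treatment starts. Where order matters the protocol says so in words, as for staining after breakup time and pressure after fluorescein. The section 9 table places symptoms and OSDI above every examination row, although it is not chronological either. This stands: the problem is conditional on how sites read 11.2. It does not remove the point, because nothing in the protocol requires the questions before the drops.

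Four further replies stand and limit the point:
- OSDI has a one-week recall, and the illustration models only a binary symptom, so no OSDI effect is shown.
- Section 10.4 asks about symptoms related to pterygium, so some investigators will not ask about sensation at that moment.
- Section 14 names no visit for its intra-group tests, so a Day 7 or Day 15 test is possible but not specified.
- Section 14 names chi-squared or Fisher tests, not McNemar, and section 7.2 lets both eyes of a subject count as cases, so the independence used in the illustration is doubtful.

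A reader might infer that change from baseline is confounded with anaesthesia as a matter of fact, or that the randomised comparison is biased in favour of the drug. The documents support neither. The first needs sites to follow an order that is not stated to be binding. The second fails because both arms share the same visit procedures, so equal masking dilutes a difference and does not create one.

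**Conclusion.** The point holds as a conditional risk, confined to Days 7 and 15 and mainly to burning and foreign body sensation. It assumes that sites follow the listed order, that subjects answer about the present state of the eye, and that tetracaine masks some symptoms to a similar degree in both arms. The consequences are then spurious within-group improvement and diluted between-arm differences at two interim visits.

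The documents give no symptom prevalence, persistence between visits or degree of masking, so the size cannot be derived; every percentage in the working is illustrative. The outcomes affected are secondary or tolerability outcomes. Severity is minor, and the change is a free improvement.

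**What to change.** In section 11.2, move OSDI and the symptom enquiry ahead of the ophthalmic exploration, matching 11.1 and 11.3. Add one sentence to section 11 stating that both are completed before any drop or dye is instilled, at every visit. A recall window for the symptom enquiry in 10.4 would also help.

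The cost is reordering two lines and adding a sentence. Sample size, visits and resources are unchanged. The change works only for visits that have not yet taken place.
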